### 4.8.5 Vital Signs

Descriptive statistics (mean, standard deviation, median, and range) for vital signs data, including systolic and diastolic blood pressure, heart rate, respiration rate, and body temperature, will be calculated for the raw data and for their changes from baseline at each scheduled assessment.

All vital signs data will be listed together with body weight.

### 4.8.6 ECOG Performance Status

ECOG results will be summarized using shift from baseline. All ECOG data will be listed.

### 4.9 Efficacy Analyses

Due to the early termination of the trial, efficacy data will be listed only. Disease assessment (CR, CRi, PR, PD, NR or NE) data will be listed.

### 4.10 Pharmacokinetic Analyses and Pharmacodynamic Analyses

The actual blood sampling time and actual amount of dose administered will be recorded and used in calculation of PK parameters. All PK samples will be evaluable as long as the actual collection times are recorded. Analysis of the ADCT-402 total antibody [drug-to-antibody ratio (DAR>0)], PBD-conjugated antibody (DAR≥1), and SG3199 (unconjugated warhead) concentrations in serum will be analyzed using a noncompartmental analysis method. The PK parameters from analysis will include maximum concentration ( $C_{max}$ ), time to  $C_{max}$  ( $T_{max}$ ), area under the concentration-time curve from time zero to the last quantifiable concentration ( $AUC_{0-last}$ ), area under the concentration-time curve (AUC) from time zero to the end of the dosing interval ( $AUC_{0-\tau}$ ), area under the concentration-time curve from time zero to infinity (AUC), accumulation index (AI), apparent terminal half-life ( $T_{1/2}$ ), apparent systemic clearance (CL), and volume of distribution at steady state ( $V_{ss}$ ).

Data presentation by tables will include individual patient concentrations by nominal time, individual PK parameters, statistical summaries for concentrations by dose cohort and nominal time, and statistical summary for PK parameters. Data presentation by figures will include individual patient concentrations by actual time, and mean (standard error) of concentrations by nominal time.

At selected times as indicated in the schedule of events tables, samples for ADCT-402 antidrug antibodies (ADA) were also collected concurrently with the PK samples. Results from ADA testing will include tabular summarization for number/proportion of patients with positive pre-dose ADA response, number of patients with post-dose ADA response only, and number of patients with positive ADA response at any time. The denominator will be the total number of patients tested for ADAs in the study. For instances in which a positive ADA titer is observed, results from testing for neutralizing antibody potential will be reported.

## 5 Interim Analyses

NA

## 6 Data handling conventions

### 6.1 General conventions

#### 6.1.1 Missing data

##### Handling of missing relationship to investigational product of AEs

If the assessment of the relationship to investigational product is missing, then the relationship to investigational product has to be assumed and the AE considered as such in the frequency tables of possibly related AEs, but no imputation should be done at the data level.

##### Handling of missing severity/grades of AEs

If the severity/grade is missing for one of the treatment emergent occurrences of an AE, the maximal severity of the remaining occurrences will be considered. If the severity is missing for all the occurrences a “missing” category will be added in summary table.

No other imputation of values for missing data will be performed.

#### 6.1.2 Unscheduled visits

Unscheduled visit measurements of laboratory data will be used for computation of baseline and worst values and/or grades. Re-windowing for unscheduled visits will not be performed.

#### 6.1.3 Duplicated visit

Depending on the statistical analysis method, single values may be required for each analysis window. For example, change from baseline by visit usually requires a single value per visit. Unless otherwise noted throughout the rest of this document, when a single value is needed, the following rule(s) will be used:

- If more than 1 assessment occurs during the same nominal visit, select the record closest to the nominal day for that visit.
- If there are 2 assessments that are equidistant from the nominal day, the data of the assessment after the scheduled study day will be used.
- The last measurement will be used if multiple measurements are taken on the same day.

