4.1.2 Day 1 (\pm 3 days) of Each Cycle

Day 1 of each cycle occurs on infusion day. The following procedures will be performed prior to ADCT-402 infusion (unless otherwise indicated) at each cycle.

- Serum or urine β -HCG pregnancy test (women of child-bearing potential, Cycle 1 only) required if the screening pregnancy test was obtained >7 days prior to Day 1.
- Physical examination, including whole body skin assessment, unless an assessment was performed within 3 days prior to Day 1.

ADCT-402-102 Protocol Amendment 3

• Vital signs: On Day 1 of Cycles 1 and 2, vital signs are to be measured before the start of ADCT-402 infusion, every 30 minutes during the infusion, at the end of infusion, and at 1, 3, and 6 hours after the end of infusion. If no clinically significant changes occur during the Cycles 1 and 2, vital sign measurements are to be obtained prior to the start of and at the end of ADCT-402 infusion for all subsequent cycles. If clinically significant changes in vital signs are observed at Cycle 1 and/or 2 infusion, that patient will be required to have vital signs measured before the start of the ADCT-402 infusion, every 30 minutes during the infusion, at the end of infusion, and at 1, 3, and 6 hours after the end of the ADCT-402 infusion for all subsequent cycles.

- Weight, unless an assessment was performed within 3 days prior to Day 1.
- ECOG performance status.
- Hematology, coagulation panel, and biochemistry parameters, will be measured prior to dosing unless the last sample was collected:
 - o <24 hours before the start of ADCT-402 infusion on Day 1 of Cycle 1, or
 - <72 hours before the start of ADCT-402 infusion on Day 1 of Cycle 2 and subsequent cycles.
 

- Sample collection for
 - o Additional renal function studies
 - Urinalvsis

Prior to dosing unless the last sample was collected:

- o <24 hours before the start of ADCT-402 infusion on Day 1 of Cycle 1, or
- <
- 12-lead ECG (Cycles 1 and 2) before the start of the ADCT-402 infusion, within 30 minutes of the end of infusion, and 3 hours (± 30 minutes) and 24 (± 2.4) hours after the end of infusion (Table 5 and Table 7 in Appendix 12.1). For Cycle 3 and subsequent cycles, a 12-lead ECG is to be performed before the start of ADCT-402 infusion.
- Sample collection for central laboratory analysis of ADA (all cycles).

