7.6.1.3 Additional Safety Assessments

The results of scheduled assessments of cytokine levels, vital signs, physical examinations, ECOG performance status, and 12-lead ECGs will be summarized. All data will be reported according to the nominal visit date for which it was recorded (i.e., no visit windows will be applied). Unscheduled data will be included in "worst case" summaries, which will capture a worst case across all scheduled and unscheduled visits after the first dose of study treatment. All data will be listed. Further details will be provided in the SAP.

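### SAP 6.1.3 states no exception to its last-of-the-day rule for the planned Day 1 readings, and the protocol's worst-case summary is missing for vital signs and ECG heart rate

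*SAP*

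**What the plan says.** SAP 6.1.3 is a general convention that is not tied to any data type. It opens: "Unless otherwise noted throughout the rest of this document, when a single value is needed, the following rule(s) will be used". Its own example is the analysis at issue: "For example, change from baseline by visit usually requires a single value per visit". Three rules follow: take the record nearest the nominal day; if two are equally near, take the later; and "The last measurement will be used if multiple measurements are taken on the same day".

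Protocol 4.1.2 sets out a planned series on Day 1 of Cycles 1 and 2. Vital signs are taken before the infusion and then "every 30 minutes during the infusion, at the end of infusion, and at 1, 3, and 6 hours after the end of infusion". ECGs are taken before the infusion, near its end, and 3 and 24 hours after it; the 24-hour ECG belongs to Day 2 (protocol 4.1.3). From Cycle 3, vital signs are taken before and at the end of infusion, except that patients with clinically significant changes in Cycle 1 or 2 keep the full series. The ECG is then pre-dose only.

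SAP 4.8.5 says that vital-sign statistics "will be calculated for the raw data and for their changes from baseline at each scheduled assessment". SAP 4.8.4 has the equivalent for ECG heart rate. Neither section says whether an assessment is a visit or a time point within a visit.

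Protocol 7.6.1.3 covers vital signs and 12-lead ECGs among other assessments. It promises worst-case summaries, "which will capture a worst case across all scheduled and unscheduled visits after the first dose of study treatment". In the SAP, section 4.8.3 carries this over for laboratory data, and 6.1.2 adds: "Unscheduled visit measurements of laboratory data will be used for computation of baseline and worst values and/or grades". Section 4.8.4 tabulates QTc categories at any post-baseline point. No worst-case summary is given for vital signs or ECG heart rate.

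**The concern.** Two gaps meet here. The tie-breaking rule, taken literally, chooses the Day 1 reading furthest from the infusion and leaves the earlier post-start readings out of the by-visit tables. The summary that would have caught an extreme value whenever it occurred is also not in the SAP for these variables.

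A transient fall in blood pressure, rise in heart rate or fever that settles within 6 hours, and that the investigator does not report as an adverse event, could then be absent from every summary table. Safety is a primary objective, and under this SAP efficacy is only listed, so the safety tables are its main output.

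Rows for different cycles would also refer to different times since infusion, so a trend across visits could reflect timing alone.

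**Working it through.** The plan gives no figure to reproduce. The check applies the rules of SAP 6.1.3 to the reading times in protocol 4.1.2.

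**Inputs.** Vital-sign times: pre-dose, every 30 minutes during infusion, end of infusion (EOI), EOI+1 h, +3 h, +6 h. Day 1 ECG times: pre-dose, EOI, EOI+3 h. Infusion length: 1 hour at first, and 30 minutes allowed later if well tolerated (protocol 3.1 and 5.3). Baseline: the last non-missing value up to first dose (SAP 4.8).

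**Applying the rules by visit.** All Day 1 readings fall on the same day, so the nearest-day rule and the equidistant rule cannot separate them. The third rule decides and keeps the last.

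| Day 1, Cycles 1–2 | Planned readings | After start | Kept | Left out after start |
|---|---|---|---|---|
| Vital signs, 1-hour infusion | pre, 30 min, EOI, +1, +3, +6 h = 6 | 6 − 1 = 5 | 1 (+6 h) | 5 − 1 = 4 |
| Vital signs, 30-minute infusion | pre, EOI, +1, +3, +6 h = 5 | 5 − 1 = 4 | 1 (+6 h) | 4 − 1 = 3 |
| ECG heart rate | pre, EOI, +3 h = 3 | 3 − 1 = 2 | 1 (+3 h) | 2 − 1 = 1 |

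In Cycle 1 the pre-dose reading is normally used as baseline, so it is not lost.

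**Later cycles.** For patients without earlier significant changes, the last vital-sign reading is EOI. For patients with them, it is still EOI+6 h. One Cycle 3 row would therefore mix readings 6 hours apart in time since infusion. The ECG row moves from 3 hours post-infusion to pre-dose.

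**Applying the time-point reading.** If each planned time point is an assessment, nothing is a duplicate and nothing is left out.

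**Illustration (assumed values, not from the documents).** Take systolic pressure of 120 at baseline and 88 at EOI, the lowest reading. If it recovers to 119 at +6 h, the by-visit change is 119 − 120 = −1, while the worst change is 88 − 120 = −32. If it stays at 88 to +6 h, both are −32. The understatement thus runs from 0 to about 31, depending on recovery.

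**Worst-case summary, protocol against SAP.** Laboratory data: promised and present. QTc: promised, and in effect present through the any-post-baseline table. Vital signs and ECG heart rate: promised and absent. SAP 3.3 says that analyses are selected or modified and points to each section for details, but 4.8.4 and 4.8.5 declare no such omission. SAP 4.9, by contrast, states openly that efficacy is listed only.

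**The case against.** The best defence is that the rule is conditional. It applies only where a single value is needed and gives way to anything noted elsewhere, under a heading about duplicated visits. The 30-minute, EOI and later readings are each scheduled, so they can be read as separate assessments. SAP section 4 also says that all available data are used. This stands: a reader might infer that the SAP certainly reduces Day 1 to one value, and the text does not go that far. The defect is an unstated exception, which two programmers could resolve differently.

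A reader might also infer that infusion-time changes vanish from the report. The documents do not support that. SAP 4.8.4 and 4.8.5 list all ECG and vital-sign data. Protocol 6.3.6 and 6.3.8 require clinically significant abnormalities to be recorded as adverse events. SAP 4.8.2.1 tabulates and lists infusion-related reactions. Adverse-event capture does, however, depend on an investigator's judgement and does not replace a summary of measured values.

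Three further inferences go too far. Worst-case reporting is not lost for all ECG data, because QTc has its table. SAP 6.1.2 says that unscheduled laboratory data are used, but it does not say that other unscheduled data are excluded. And not every patient switches to EOI readings after Cycle 2.

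Finally, the trial ended early, the analysis is descriptive, and reduced scope is announced. That could justify dropping the table, but the SAP does not say that it was dropped.

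**Conclusion.** The point holds in a limited form. Read by visit, SAP 6.1.3 leaves 3 or 4 post-start vital-sign readings and 1 ECG heart-rate reading out of each Day 1 summary in Cycles 1 and 2, and later vital-sign rows mix times since infusion. This depends on the by-visit reading, which the SAP's own example favours but its wording does not compel.

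The missing worst-case summary for vital signs and ECG heart rate does not depend on that reading. It is a departure from protocol 7.6.1.3 that SAP 3.3 does not name.

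The consequence is confined to summary tables and to changes not reported as adverse events. The documents do not show how many such changes there are. The correction is worth making because it is cheap and concerns the trial's main remaining output.

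**What to change.** - SAP 6.1.3: limit the last-value rule to repeat readings at the same planned time point.
- SAP 4.8.4 and 4.8.5: summarise Day 1 ECG heart rate and vital signs by planned time point, with change from the baseline already defined in SAP 4.8.
- SAP 4.8.4 and 4.8.5: add the worst post-baseline value per patient (minimum and maximum, including unscheduled readings) for vital signs and heart rate, by dose level, as protocol 7.6.1.3 provides. If the sponsor prefers not to, name the omission and its reason in SAP 3.3; that would make the departure open but would not close the gap in the tables.

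The cost is a few sentences in the SAP, more table rows and one extra table. The readings are already in the protocol's schedule, so no new data are needed.
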